The University of Texas Southwestern Medical Center at Dallas Institutional Review Board

PROJECT SUMMARY

Principal Investigator:

[name], PT, DPT, PhD

Study Title:

Scoliosis-Specific Exercises for At-Risk Mild AIS Curves: A Multi-Site Preliminary Randomized Trial

Sponsor/Funding Source:

Scoliosis Research Society

Purpose:

To investigate the feasibility and short-term effectiveness of scoliosis specific exercises as part of a multi-center randomized controlled trial in patients with mild AIS curves at the greatest risk of progression. Specifically, our study aims are as follows:

Aim 1: The primary aim is to assess the feasibility of a multi-site prospective randomized controlled trial in skeletally immature patients with mild AIS curves at high risk of progression. Participants instructed in scoliosis-specific exercises (SSE) provided by physical therapists certified in the Schroth-based method (SSE group) will be compared to the standard-of-care of observation (control group).

Feasibility will be evaluated according to participant:

1) recruitment rate at each site (measured by the number of participants enrolled per month at each site)

2) overall recruitment rate (measured by the total number of participants enrolled after 1 vear)

3) treatment attendance in the SSE group (measured by the percentage of prescribed hours of physical therapy sessions attended)

4) home exercise adherence in the SSE group according to weekly e-mails (measured by the percentage of prescribed exercises completed from baseline to 1 year)

5) home exercise adherence in the SSE group according to a smartphone application (measured by the percentage of prescribed exercises completed from baseline to 1 vear)

6) home exercise adherence in the SSE group according to an exercise log (measured by the percentage of prescribed exercises completed from baseline to 1 year)

Aim 2: The secondary aim is to assess whether scoliosis-specific exercises (SSE) will be more effective in skeletally immature patients with mild AIS curves at high risk of progression, Current Protocol 4.19.2019.docx

Page 1 of 13

compared to the standard-of-care of observation (control).

The outcome quantifying the effect of 1 year of physical therapy intervention will include:

1) curve magnitude (measured by the Cobb angle on radiograph at baseline and 1 year)

2) curve progression (measured by whether the curve progresses >5° after 1 year)

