3) brace prescription (measured by the percentage of participants prescribed a brace after 1 year)

Background:

Adolescent idiopathic scoliosis (AIS) is a three-dimensional deformity of the spine, affecting 1-3% of children ages 10-16 years.¹ Adolescents with AIS have the highest risk of curve progression during the period of rapid growth prior to achieving skeletal maturity.¹ Patients who are Risser 0 are at greatest risk for curve progression.² The standard medical management for AIS in the United States (US) includes observation for skeletally immature mild curves, bracing for skeletally immature moderate curves, and surgery for severe curves.

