lacking. Given the persisting uncertainty among medical professionals regarding the true potential of SSE, the purpose of this trial is to objectively and rigorously evaluate SSE compared to observation (standard-of-care). The results from this trial will provide much needed high-quality evidence regarding the feasibility and efficacy of SSE. In particular, this study will limit the inclusion criteria to skeletally immature patients with mild AIS curves. These patients are at highest risk of curve progression and have a greater potential for a meaningful effect with early intervention before their growth spurt and curve acceleration phase. Many families hope to avoid the need for bracewear.⁸ A smaller curve is more flexible²⁸ and may be more amenable to changes from exercise, especially before spinal growth is complete. In particular, mechanical wedging of the immature disc and vertebral body may still be reversible.²⁹

Concise Summary of Project:

This study will be a multi-center, dual-arm randomized control study evaluating skeletally immature patients with mild AIS curves. At six institutions, patients will be randomized into either the scoliosis-specific exercise (SSE) treatment arm or a control group. The SSE group will receive training in SSE, posture, and activities of daily living by physical therapists certified in Schroth-based exercise methods. The control group will not receive SSE instruction and will only be observed by their treating orthopaedic surgeon (which is considered the standard-of-care treatment method). Results will be compared after one year of treatment.

Study Procedures:

All patients with AIS meeting the following inclusion criteria will be eligible to participate in this trial: diagnosis of AIS; ages 10 to 17 years; major curve Cobb angles 12° to 24°; thoracolumbar, lumbar, or primary thoracic curve patterns; and Risser grade 0. Patients will be excluded according to the following exclusion criteria: scoliosis other than AIS, upper thoracic or double curve patterns, developmental disorders that prevent understanding and compliance with an exercise schedule, current or previous brace wear, and previous participation in a SSE program, previous spine surgery, inability to commit to performing a home exercise program for 15 minutes a day, 5 days a week, and inability to commit to attend at least 8 hours of PT within 6 months.

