All patients diagnosed with Adolescent Idiopathic Scoliosis who meet the following inclusion criteria will be eligible to participate in this trial:

- 1) Age 10 to 17 years
- 2) Major curve Cobb angles of 12° to 24°
- 3) Compensatory curve should be less than 5° of the main curve (ex: 10° if the main curve is 15° or 15° if the main curve is 20°)
- 3) Risser Grade 0
- 4) Single thoracic, thoracolumbar, or lumbar curve patterns

Criteria for Exclusion of Subjects:

Patients will be excluded according to the following exclusion criteria:

- 1) Scoliosis other than AIS (congenital, neuromuscular, etc)
- 2) Upper thoracic or double curve patterns
- 3) Diagnosis of a developmental disorder that prevents understanding and compliance with an exercise schedule
- 4) Current or previous brace wear
- 5) Previous participation in a SSE program
- 6) Previous spine surgery
- 7) Patient inability to commit to attend at least 8 hours of PT within 6 months

Sources of Research Material:

Current Protocol 4.19.2019.docx Page 7 of 13 After the consenting process, patient demographics will be collected from the patient chart. All demographic information, clinical, and radiographic measurements will be recorded after informed consent is obtained during the patient's appointments.

Texas Scottish Rite Hospital will serve as the lead institution for this study and will create/maintain a REDCap database to house all study data. All other participating sites will obtain IRB approval from their own institutions and will enter into a Data Use Agreement contract with Texas Scottish Rite Hospital in order to access the database and run data analysis. Only a limited data set will be shared between the institutions, and all patient information will be entered into the database in a de-identified fashion. The data to be shared between institutions includes:

- Patient study number (to be generated for each institution in a de-identified format through REDCap)
- Date patient is consented to the study
- Date physical therapy/control status is initiated
- Age
- Initial curve Cobb angles
- Risser sign
- De-identified x-ray images (AP and Lateral views)
- Height, Weight, and BMI
- Physical activity level
- Curve pattern (classification as thoracic, thoracolumbar, or lumbar)
- Schroth curve pattern
- Trunk rotation
- Triradiate status
- Menarchal status
- SRS-22
- 3 question parent survey about attitudes toward SSE, posture, and scoliosis

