All information obtained through medical and radiographic records will be reviewed solely by the primary investigators, co-investigators, and other study team personnel. Publically reported information will be in the form of a statistical summary only: no information will be divulged that could be linked to a specific patient involved with the study. No patient information will be disclosed outside of the study team. The University of Texas Southwestern Medical Center Institutional Review Board may review the research information for auditing purposes. The team will keep the consents and study files in both a locked cabinet as well as electronic copies within the electronic study folder (this folder will be stored on password encrypted hard drive which may be accessed by members of the study team only). All other electronic data collected will be stored on a password protected electronic database with access limited to the study team.

Procedures to Maintain Confidentiality:

All normally used means for protecting patient confidentiality will be strictly followed. All consents, clinical and radiographic measurements, and patient demographics will be stored in a secure electronic database. This database will be password protected and access will be limited to only individuals on the study team. Data will be de-identified for each patient by assigning a Study ID in the database. All PHI and the unique study ID for each patient will be stored in a separate password-protected and encrypted spreadsheet that only members of the study team at TSRH will have access to. Only a statistical summary of the information will be published: at no time will any data published include information that can be linked to a study participant. All requirements for HIPAA compliance in regards to patient confidentiality will be followed and the University of Texas Southwestern Medical Center's Institutional Review Board will have the right to inspect all medical records related to this study for the purpose of ensuring patient confidentiality.

Current Protocol 4.19.2019.docx Page 10 of 13

Biostatistics

Continuous variables will be summarized with means, standard deviations and ranges and analyzed using student t-tests; categorical variables will be summarized as counts and percentages and analyzed using Fischer's exact tests. Data will be checked for normality and equal variance.

Potential Benefits:

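### No masking is specified for whoever reads the Cobb angle, so two of the three Aim 2 outcomes are open to differential reading error, mainly at 1 year

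*Combined protocol and SAP*

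**What the plan says.** The Purpose section lists three outcomes for Aim 2. The first is "curve magnitude (measured by the Cobb angle on radiograph at baseline and 1 year"), the second is "curve progression (measured by whether the curve progresses >5° after 1 year"), and the third is "brace prescription (measured by the percentage of participants prescribed a brace after 1 year"). The first two come from the same angle reading. The third is a treatment decision.

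On how the angle is obtained, Sources of Research Material says that all demographic information, "clinical, and radiographic measurements will be recorded after informed consent is obtained during the" patient's appointments. Subject Safety and Data Monitoring adds: "All information obtained through medical and radiographic records will be reviewed solely by the primary investigators, co-investigators, and other study team personnel". Under Study Procedures, the study team includes the certified therapists who deliver the exercises. The x-rays are those of routine care visits.

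No section names the reader or says whether the reader knows the arm. The only mention of blinding anywhere is in the title of a cited study in the reference list.

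The list of data shared between institutions includes "De-identified x-ray images (AP and Lateral views"), to be held in a database kept by the lead site. The list gives no time point for these images, and the only Cobb value on it is the initial one. No use of the shared images is described.

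**The concern.** The arms are supervised exercise and no treatment, so patients and treating staff know the allocation. Exercise patients may also meet their therapist at return-to-clinic visits, the same kind of visit at which measurements are said to be recorded. The Anticipated Results section predicts a benefit of exercise on all three Aim 2 outcomes. A manual angle reading made in that setting can drift by arm without anyone intending it.

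Progression is a threshold on the same angle, so one drift moves both outcomes in the same direction. A reader of the results could take that as two findings in agreement. The Background gives the trial's purpose as to "objectively and rigorously evaluate SSE compared to observation", and significance tests are planned on these outcomes. An unmasked reading would weaken that comparison where it could be protected at little cost.

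**Working it through.** The documents give no sample size calculation, alpha, SD or effect size, so there is no figure of the plan's own to reproduce. The calculation below only shows how large an effect a small reading tilt could have.

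**Inputs from the documents**
- Six institutions (Concise Summary of Project) and a recruitment benchmark of at least 18 per site after 1 year (Anticipated Results): 6 × 18 = 108.
- 2:1 allocation (Recruitment Methods and Consenting Process): 72 SSE and 36 control.
- t-test for continuous outcomes and Fisher's exact test for categorical ones (Biostatistics).
- A 50% risk of progression of 5° or more in Risser 0 and 1 patients with curves of 15 to 30° (Background). It is used as one control rate for illustration.

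**Assumptions not in the documents**
- Two-sided 5% tests, no dropout and no true effect.
- SD of 1-year change of 4, 5 or 6°, with change normally distributed.
- Every SSE change read lower by b = 1° or 2°.

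**Cobb change, t-test.** SE = SD × √(1/72 + 1/36) = SD × 0.2041, noncentrality = b/SE, 106 degrees of freedom.

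| SD | SE | b = 0° | b = 1° | b = 2° |
|---|---|---|---|---|
| 4° | 0.816° | 5.0% | 22.8% | 68.0% |
| 5° | 1.021° | 5.0% | 16.3% | 49.3% |
| 6° | 1.225° | 5.0% | 12.8% | 36.6% |

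At SD 5° and b = 1°, for example, the noncentrality is 1/1.021 = 0.98, which gives 16.3%.

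For scale, the difference detectable with 80% power at 72:36 is (1.960 + 0.842) × SE, which is 2.29°, 2.86° and 3.43° for SD 4, 5 and 6°. A tilt of 1 to 2° is a sizeable part of that.

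**Progression >5°, Fisher's exact test.** With a control rate of 50%, mean change is 5° and the apparent SSE rate is P(N(5 − b, SD) > 5). Rejection probabilities are exact.

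| SD | SSE rate, b = 1° | Rejects | SSE rate, b = 2° | Rejects |
|---|---|---|---|---|
| 4° | 40.1% | 12.9% | 30.9% | 42.3% |
| 5° | 42.1% | 9.5% | 34.5% | 28.2% |
| 6° | 43.4% | 7.8% | 36.9% | 20.4% |

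With no tilt the test rejects in about 4.0% of trials. If mean change is 3° instead, a 1° tilt opens a gap in progression of 8.2, 7.0 and 6.1 points (SD 4, 5, 6°), and Fisher's test rejects in about 13%, 10% and 8%.

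**Both outcomes together** (mean change 3°). Both tests are significant in about 10%, 7% and 5% of trials at a 1° tilt, and in about 36%, 25% and 18% at 2°.

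**Which reading is exposed.** Cobb 12 to 24° is an entry criterion. Eligibility review and consent come before assignment in Study Procedures, so the eligibility reading is made before there is an arm to know. The exposure lies mainly in the 1-year reading.

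**The case against.** A reader might infer that the protocol has Cobb angles measured open-label. It does not say so. The sentence on recording describes when data are collected, and its closing words about appointments could attach to the obtaining of consent. Nothing states who reads the film or what that person knows. The plan is equally silent on the purpose of the shared images, so a central reading is neither planned nor excluded. This stands, and it limits the point to masking not being specified.

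A reader might also infer that the films needed are already held. The shared list gives no time point, so this is not shown for the 1-year film, the one that matters most.

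Nor would pooling remove the bias by itself. The same data set carries the start date of therapy or control status and the therapy hours attended, and study numbers are generated by institution. De-identified is not masked.

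The direction of any tilt is also undocumented. The investigators expect benefit, but routine assessment is by orthopaedic surgeons, and the Background describes physicians in the US as not widely prescribing therapy for this condition. Apparent agreement between the two outcomes is a modest risk at 1° and becomes substantial only at 2°.

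Finally, the trial is preliminary and its primary aim is feasibility. None of the six feasibility measures uses the Cobb angle. That lowers the weight of the point but does not answer it, because the protocol also promises high-quality evidence on efficacy and plans tests of it.

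**Conclusion.** The point holds in limited form. The protocol specifies no masking of the Cobb reader in a trial whose treating staff know the arm, and two of three secondary outcomes depend on that reading. The feasibility conclusions are untouched, and brace prescription is outside this point.

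At 72:36 with SD 4 to 6°, a uniform 1° tilt favouring SSE takes the false-positive rate of the Cobb t-test from 5% to 13 to 23%, and a 2° tilt takes it to 37 to 68%. For progression at a 50% control rate, Fisher's test goes from about 4% to 8 to 13% and 20 to 42%. These figures show sensitivity. They do not estimate bias in this trial: the tilt, its uniformity, its direction and the SD are all assumed, and 108 is a feasibility benchmark with no dropout taken off. The documents do not support a claim that biased reading will occur, only that the plan leaves it possible. The change should be made because it is cheap.

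**What to change.** State in the protocol that:
- de-identified baseline and 1-year films are both uploaded to the shared database from all six sites;
- the analysed Cobb angles are read from these films, in random order and under recoded file names, by an existing study-team member who is not treating the patients and has no access to arm, site, visit order or the therapy fields in the database;
- >5° progression is derived from these readings;
- clinic readings are kept for care only.

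At the benchmark this is 108 × 2 = 216 radiographs to measure. The cost is some hours of existing staff time, 1-year uploads from every site, recoding and restricted database access. No new visits or imaging are needed, since the Cobb outcome already requires a radiograph at both time points. The analysed values will come later than the clinic values and may differ from them. Masked reading reduces reader bias but leaves ordinary measurement error and does nothing for brace prescription.

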Patient medical records will be reviewed for eligibility. If a patient is deemed eligible for inclusion in the study, a member of the research team will meet with the patient and his or her family to review the consent form in a private medical exam room. The family will be given ample time to review the consent form and ask any questions. If a participant chooses to participate, a consent form will be signed by both the patient and the legal guardian prior to any investigational procedures occurring.

Once a consent form has been signed, patients will be randomly assigned by the TSRH on site statistician to one of the two following groups:

1) Standardization of Physical Therapy:

Current Protocol 4.19.2019.docx Page 4 of 13 Physical therapists from Texas Scottish Rite Hospital, Boston Children's Hospital, Columbia University Medical Center, Norton Leatherman Spine Center, Johns Hopkins University, and Texas Children's Hospital who received training and certification in the Schroth-based (BSPTS) method have been recruited as members of the study team. Physical therapists at each institution will deliver a standardized exercise intervention.

2) Study Groups:

A) Scoliosis-Specific Exercise (SSE) Group

Each patient assigned to the SSE group will attend at least 8 hours of supervised exercise training led by a Schroth-based certified physical therapist over the course of 6 months. Ideally, patients will be seen for 7 sessions:

- 1) First session: 2 hours
- 2) Session 2: 1 hour (1 week later)
- 3) Session 3: 1 hour (1-2 weeks later)
- 4) Session 4: 1 hour (2-3 weeks after Session 3)
- 5) Session 5: 1 hour (3-4 weeks after Session 4)
- 6) Session 6: 1 hour (1-2 months after Session 5)
- 7) Session 7: 1 hour (1-2 months after Session 6)

The exact number of training sessions and time frame will be determined by the patient's ability to perform the exercises. All therapists will use a standardized exercise prescription algorithm and performance checklist similar to [name] scoliosis exercise study. Patients will perform a home exercise program for 15 minutes a day, 5 days a week, when they can independently execute their prescribed exercises according to the following criteria:

1) Correctly move the pelvis so the body weight is over the base of support and neutral.

2) Accurately set up exercises per curve pattern in different positions. Exercises progress from static to dynamic and passive to active corrections.

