3) Proficiently perform a minimum of 8 exercises integrating scoliosis-specific corrections which include auto-elongation to increase the spaces between the pelvis, vertebrae, and ribs. Various kinesthetic, mental imagery and proprioceptive strategies are used to further open concavities and depress convexities.

4) Perform scoliosis-specific corrections during activities of daily living. The overall goal is for patients to maintain a corrective posture throughout the day.

Patients will be asked to use a smartphone or tablet application (app) when performing the home exercise program which will be one method of tracking exercise adherence. A paper version of the app will be available to patients without access to a smartphone or tablet. Patients will also be sent electronically via email that is collected with a demographic intake form on the patient's initial visit, a weekly survey regarding home exercise adherence through a secure research database, the Research Electronic Data Capture (REDCap). An exercise log initialed by the guardian will help families keep track of their exercise adherence and serve as a way to monitor exercise adherence for patients who may not have a smartphone, tablet, or computer.

Current Protocol 4.19.2019.docx Page 5 of 13 Patients will also be able to meet with the therapists at their return-to-clinic visits and every 2-3 months thereafter until their 1 year follow-up to assess performance quality, maintain motivation, and progress intensity. Patients may be withdrawn if they do not maintainexercise adherence within 6 months.

B) Control Group

Patients randomized to this group will continue receiving standard-of-care treatment from their orthopaedic physician which includes regularly scheduled clinic visits and observation. Observation consists of no treatment of the scoliosis, only routine clinical assessment by the orthopaedic surgeon to detect curve progression every 3 to 6 months.

Once all measurements have been collected at the patient's enrollment and one year followup, patients in this group will continue to be tracked through observation until skeletal maturity in order to record whether the patient experienced curve progression, was prescribed a brace, or proceeded to surgical treatment.

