Eligible patients will be screened based on the research coordinator's review of the scoliosis clinics at TSRH or from the recommendation of the patient's treating physician. The Investigators in this study will have the ability to suggest their own patients. Once deemed eligible, a member of the study team will meet with the patient and his or her legal guardians in order to review the consent form. The patient and family will be given ample time to review the consent form and ask any questions. In order to respect the privacy of potential patients, all consenting procedures will occur in a private clinic exam room. The research coordinator will explain to the family that their participation in the study is voluntarily and they will receive their participation (or lack of) in the study will not affect their standard treatment or relationship with their treating physician. Appropriate patient assent and caregiver consent will be obtained by a member of the study team prior to any study activities occurring (per IRB protocol) Patients meeting the study criteria who consent to participate will be randomly assigned to either the treatment or control arm in a 2:1 ratio. Patients will be assigned a group using a block-randomized, within site method. Patient assignment will be done by utilizing a computer-generated list and pre-sealed envelopes that will be distributed to the participating sites before enrollment. The list and envelopes will be generated by the statistician at Texas Scottish Rite Hospital.

If an eligible patient is missed in clinic whom the research team has an existing relationship with through a medical staff member on the study team, they may be contacted by a member of the research team via phone. The patient family will be identified and then told the following:

Schroth Ex-Trial Phone Solicitation Script:

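### Site-held pre-sealed envelopes and assignment by the lead-site statistician after consent need one reconciled procedure; central release would cheaply reduce the room for foreknowledge

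*Combined protocol and SAP*

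**What the plan says.** Two sections of the combined protocol and SAP describe how a patient gets an arm.

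- **Study Procedures:** "Once a consent form has been signed, patients will be randomly assigned by the TSRH on site statistician".
- **Recruitment Methods and Consenting Process:** the ratio is 2:1 and "Patients will be assigned a group using a block-randomized, within site method". The mechanism is then given: "Patient assignment will be done by utilizing a computer-generated list and pre-sealed envelopes that will be distributed to the participating sites before enrollment". On preparation: "The list and envelopes will be generated by the statistician at Texas Scottish Rite Hospital".

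The setting matters as well.

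- There are six sites: "At six institutions, patients will be randomized into either the scoliosis-specific exercise (SSE) treatment arm or a control group".
- The arms are visibly different. One receives supervised exercise; for the other, "Observation consists of no treatment of the scoliosis, only routine clinical assessment by the orthopaedic surgeon".
- On who may put patients forward, the recruitment section says: "The Investigators in this study will have the ability to suggest their own patients".
- Under Sources of Research Material, the lead institution "will create/maintain a REDCap database to house all study data", and the date of consent is among the shared data items.

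**The concern.** The two descriptions agree only if assignment by the statistician means assignment through the list that the statistician prepared. Read plainly, one has the statistician acting patient by patient after consent, and the other has every assignment lying at the site before the first patient enrols. Neither says who at a site opens an envelope. Six sites could therefore work differently while each follows the protocol.

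Assignment after consent does not close the gap, because the family is approached before consent. Someone who knows the next assignment can approach or defer a family accordingly. Two sets of results are exposed.

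- **Aim 2 (secondary):** Cobb angle, progression and brace prescription are compared between arms. The Biostatistics section plans t-tests and Fisher's exact tests without adjustment, and adjustment would not cure selection on unmeasured features.
- **Part of Aim 1:** attendance and home-exercise adherence are measured in the exercise arm only, so steering motivated families into that arm could raise them.

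**Working it through.** **1. The two sections side by side**

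| Question | Study Procedures | Recruitment Methods and Consenting Process |
|---|---|---|
| Who assigns? | Lead-site statistician | List and envelopes prepared by that statistician; opener not named |
| When? | After signed consent | After eligibility and consent |
| Where is the next assignment beforehand? | Not stated | In an envelope at the recruiting site |
| Opacity, numbering, custody, opening order, log | Not stated | Sealed; otherwise not stated |

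The stated safeguards are real: central preparation, sealing, and assignment after eligibility and consent. What they leave open is access. Anyone who opens site-held envelopes early knows every remaining assignment, whatever the block size. Anyone who takes them out of order can choose the arm. Central release removes that route because nothing is at the site to open. The documents contain nothing from which to estimate how likely such misuse is, so no amount of bias is derived for it.

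**2. Fixed-block predictability, a separate issue**

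In an open trial, staff can infer assignments from earlier ones. This is the same under envelopes and under central release. The documents give no block size and do not say that sites are told it, so the sizes below are assumptions.

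For a 2:1 block with *a* exercise and *b* control places, an assignment is certain once only one arm remains. For a recruiter who knows a fixed block size and sees all earlier assignments:

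certain share = [a/(b+1) + b/(a+1)] / (a+b)

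- Size 3 (a=2, b=1): (2/2 + 1/3)/3 = 0.444
- Size 6 (a=4, b=2): (4/3 + 2/5)/6 = 0.289
- Size 9 (a=6, b=3): (6/4 + 3/7)/9 = 0.214
- Size 18 (a=12, b=6): (12/7 + 6/13)/18 = 0.121

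The best-guess rate counts how often the likelier arm, given what remains, is correct. With *t* and *c* places left, the expected number of correct guesses is g(t,c) = max(t,c)/(t+c) + [t/(t+c)]·g(t−1,c) + [c/(t+c)]·g(t,c−1). For size 6, g(4,2) = 4.467, and 4.467/6 = 0.744.

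| Scheme | Known with certainty | Best guess correct |
|---|---|---|
| Fixed 6, size known | 29% | 74% |
| Randomly mixed 3/6/9, set known (simulated sites of 18) | about 3% | 73% |
| Unblocked 2:1 | 0% | 67% (2/3) |

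Varying the block size nearly removes certainty but barely changes the best guess.

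**3. If a bias illustration is wanted for fixed blocks**

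Suppose that patients steered under a certain assignment differ by an assumed *d* in one-year Cobb change, always favouring exercise. The bias is *d* times the sum of the certain shares of the two arms. Take a recruiter who does not know the size, gives equal odds to each candidate and observes 18 patients. Eighteen is the per-site feasibility benchmark under Anticipated Results, not a sample size.

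- Candidates 3, 6, 9, 18: sums of 0.14, 0.18, 0.20 and 0.22.
- Candidates 3, 6, 9, 12, 18: sums of 0, 0, 0.10, 0.001 and 0.15.

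The range is therefore 0 to about 0.2*d*. It describes block predictability and says nothing about envelopes.

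**The case against.** The strongest reply is that the plan already has a respectable method. A central statistician prepares the list, the envelopes are sealed, and assignment follows eligibility and consent. Sealed envelopes can conceal allocation, and what is missing is detail about numbering, opacity, custody and logging. That is correct, and it limits the point to an avoidable exposure.

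Opportunity is also limited. Entry is narrow and largely radiographic (Cobb 12° to 24°, Risser 0). The benchmark of 18 per site in a year is 18/12 = 1.5 patients a month, so a recruiter would seldom have several families to choose among. A coordinator reviews clinics (stated for the lead site), and families who decline after a telephone approach are noted. These facts reduce selective approach without excluding it. Investigators may still suggest patients, and whether a family can commit to the therapy hours is a judgement made before assignment.

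A reader might infer three stronger things that the documents do not support.

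- **That allocation was compromised.** Nothing in the documents shows this.
- **That the block calculations measure the harm from envelopes, or that central release would remove it.** They measure predictability that is the same under either mechanism. Nor does the closeness of 73% and 74% show that central release is the larger gain, since central release leaves the best-guess rate unchanged too.
- **That leaving the block size out of the protocol is a fault.** Withholding it from recruiting staff is sensible practice.

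**Conclusion.** The point holds as a modest, cheap improvement to a preliminary trial. Two sections give different accounts of who assigns and when, and must be reconciled. The stated site-held method leaves a route to foreknowledge that the trial's existing statistician could close. The results at risk are the Aim 2 comparisons and the exercise-arm attendance and adherence measures.

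The size of any bias from the envelopes is not known. It depends on how often envelopes would be misused and on how much steered patients would differ, and the documents inform neither. The block figures rest on assumed sizes and on a recruiter who sees all earlier assignments, and they should not be cited as the size of the envelope problem. The point does not invalidate the trial.

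**What to change.** **Preferred.** Amend Recruitment Methods and Consenting Process to follow Study Procedures. The lead-site statistician releases each assignment centrally, only after eligibility and consent are recorded, from a site-stratified 2:1 list. Use the study database if it supports this, and otherwise direct contact with the statistician. Name the same procedure in both sections.

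**If envelopes must stay.** Use opaque, sequentially numbered envelopes held at each site by existing staff who do not recruit, opened in order after consent, with a dated log. Reword Study Procedures to match.

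**With either option.** Use randomly varying block sizes recorded in a document withheld from the sites. This reduces certainty but leaves most of the guessing.

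**Cost.** Small set-up work, contact with the lead site at each enrolment, and a wording amendment at up to six IRBs, because the other sites hold their own approvals. The documents do not give enrolment status. If enrolment has begun, let assignments already made stand, apply the change only to those not yet made, retrieve unopened envelopes if moving to central release, and record and report the change date at each site. Part-used blocks may leave a small departure from 2:1.
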